3 OBJECTIVES AND ENDPOINTS

OBJECTIVES	ENDPOINTS	JUSTIFICATION FOR ENDPOINTS
Primary		
1. Investigate how TMS modulates EEG	1. Memory performance	1. Memory performance measures will allow us to

[figure not shown]
OBJECTIVES	ENDPOINTS	JUSTIFICATION FOR ENDPOINTS

neural measures of successful memory and the association of this modulation with behavioral performance
 
2. Examine how memory task state influences susceptibility to plasticity via TMS and determine the optimal neural state for improving memory
	
 • Accuracy: Percentage of successful (later remembered hit and correct rejection) vs unsuccessful (forgotten miss and false alarm) trials for item recognition (remember/familiar/new) and context recollection (spatial location) • d': Analysis of hits (correctly remembered as encoded) relative to false alarms (new objects labelled as encoded) for item recognition 
2. Late positive posterior ERP
 
 • ERP amplitude 500-700 ms after trial onset (encoding and retrieval) over parietal and occipital electrodes 
3. Theta/alpha power (secondary)
 
 • Power in the 4-13 Hz band 0-1000 ms after trial onset (encoding and retrieval) 
4. EEG functional connectivity (secondary)
 
 • Pearson correlation coefficients (r) between electrode time courses after trial onset (encoding and retrieval) 	
examine the effects of TMS on performance, as well as to sort successful vs unsuccessful trials for EEG analyses
 
2. The late positive posterior ERP has been previously shown to be a robust marker of successful memory performance²⁵
 
3. Task-induced changes in this frequency band have been previously associated with successful memory performance²⁶
 
4. fMRI functional connectivity modulation via network-targeted TMS has been previously associated with TMS-induced memory improvement. Whether EEG functional connectivity will be similarly altered, and the relevance to memory changes, remains unknown

Tertiary/Exploratory		
1. Search for MRI predictors of the	1. Baseline fMRI functional connectivity	It is hypothesized that TMS influences downstream targets

OBJECTIVES	ENDPOINTS	JUSTIFICATION FOR ENDPOINTS

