8 STATISTICAL CONSIDERATIONS

8.1 STATISTICAL HYPOTHESIS

The primary aims are to investigate how TMS alters the EEG biomarkers of successful memory performance and how memory state-related neural changes influence plasticity of the brain. Secondary aims for this protocol will include examining the MRI connectivity predictors of TMS effects.

- Primary Objective 1: Investigate how TMS modulates EEG neural measures of successful memory and the relevance of modulation to behavioral performance
 - Hypotheses
 - a. Network-targeted parietal-TMS will improve memory performance (context recollection; Primary Endpoint 1) relative to vertex-TMS trials
 - b. Relative to vertex-TMS, parietal-TMS will also increase the Late Positive Posterior ERP (Primary Endpoint 2) and theta power (Primary Endpoint 3) during encoding on successful trials, relative to unsuccessful trials
 - c. Parietal-TMS will alter EEG functional connectivity patterns (Primary Endpoint 4) at encoding during successful trials relative to unsuccessful trials
 - d. The EEG effects will correlate with memory improvement (Correlation, Primary Endpoint 1 and 2-4)
 - e. Parietal-TMS will not influence neural activity or accuracy for spatial trials, relative to vertex-TMS and no-TMS
- Primary Objective 2: Examine how memory task state influences susceptibility to plasticity via TMS and determine the optimal neural state for improving memory
 - Hypotheses
 - a. Network-targeted parietal-TMS during memory encoding will have a larger effect on memory performance (Primary Endpoint 1), relative to pre-trial parietal-TMS and vertex-TMS during encoding
 - b. Exploratory Analyses:
 - i. Parietal-TMS during memory encoding will increase the Late Positive Posterior ERP (Primary Endpoint 2) and theta-power (Primary Endpoint 3), relative to pre-trial parietal-TMS and vertex-TMS during encoding
 - ii. Additionally, parietal-TMS will alter EEG functional connectivity patterns (Primary Endpoint 4) during later-remembered trials, relative to pre-trial parietal-TMS and vertex-TMS during encoding
 - iii. Network-targeted TMS will not influence neural activity during arithmetic trials, relative to vertex-TMS and no-TMS

- *Exploratory Objective:* Determine MRI predictors of the effects of noninvasive stimulation

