8.2 SAMPLE SIZE DETERMINATION

All experiments in this protocol are powered based on the primary outcome, which relates to the effects of TMS on memory and its neural correlates.

A power analysis was conducted using G*Power v3.1.9.7. We used a repeated-measures, within-factors ANOVA based on a previous study with a similar design³⁹. Like the proposed experiments, this study delivered 2-second trains of TMS prior to trials of memory encoding or a control task and examined the effects on later memory performance and on neural activity, in this case hippocampal fMRI activity, during encoding. They used a three-way repeated-measures ANOVA to examine the interactions between TMS presence (on vs off), frequency (theta-burst vs 12.5 Hz beta), and location (parietal cortex vs supplementary motor area) and found an effect size of theta burst parietal-TMS on memory performance of $\eta^2=0.44$ and fMRI hippocampal activity of $\eta^2=0.28$. As the proposed analyses will also use three-way repeated-measures ANOVAs (see Section 8.3.2), we calculated subject number based on these effect sizes, power of 0.80, and $\alpha = 0.05$ shared across two primary outcomes, memory performance and the late positive posterior ERP ($\alpha = 0.025$ for each outcome). Thirty-two participants with complete data will be needed. To achieve $n=32$, we will recruit up to 50 subjects to account for potential non-completion (e.g., screen failure, subject withdrawal) or unusable data (e.g., due to noise).

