8.3.2 Analysis of the Primary Endpoints

- Primary Endpoint 1: Investigate how TMS modulates EEG neural measures of successful memory and the relevance of modulation to behavioral performance
This aim will examine behavioral and EEG neural outcome measures (Primary Endpoints 1-4). We will perform 3x3 ANOVAs on each outcome measure with the factors trial type (successful/ unsuccessful/ spatial), stimulation site (parietal/ vertex/ none), and their interaction. We will particularly focus on the main effect of stimulation site to determine

the influence of parietal-TMS on memory performance and its neural correlates, and the interaction effect to determine the task specificity of TMS effects. Thresholds for significant effects will be set at $p<0.025$ following FDR correction for multiple comparisons.

- Primary Endpoint 2: Examine how memory task state influences susceptibility to plasticity via TMS and determine the optimal neural state for improving memory
This aim will examine behavioral and EEG neural outcome measures (Primary Endpoints 1-4). We will perform 3x3x2 ANOVAs on each outcome measure with the factors trial type (successful/ unsuccessful/ spatial), stimulation site (parietal/ vertex/ none), stimulation timing (pre-trial and mid-trial) and their interaction. We will particularly focus on the interaction effect of stimulation site and timing to determine the influence of memory task-state parietal-TMS on memory performance and its neural correlates, and the three-way interaction effect to determine the task specificity of state-dependent TMS effects. Thresholds for significant effects will be set at $p<0.025$ following FDR correction for multiple comparisons.

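### The primary LPP model sorts memory trials by later success, which parietal-TMS is itself expected to change, so its site main effect does not isolate the effect of TMS on the LPP

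*Combined protocol and SAP*

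**What the plan says.** - Section 8.3.2, Objective 1, specifies "3x3 ANOVAs on each outcome measure with the factors trial type (successful/ unsuccessful/ spatial", crossed with site (parietal, vertex, none). Objective 2 adds stimulation timing, giving a 3x3x2 model with the same trial-type factor.
- On which effect matters, Section 8.3.2 says "We will particularly focus on the main effect of stimulation site". The interaction is there to judge task specificity.
- Section 3 says that memory performance serves to measure the TMS effect, "as well as to sort successful vs unsuccessful trials for EEG analyses". It defines the LPP endpoint as "ERP amplitude 500-700 ms after trial onset (encoding and retrieval) over parietal and occipital electrodes".
- Section 8.1, hypothesis 1a: "Network-targeted parietal-TMS will improve memory performance (context recollection; Primary Endpoint 1) relative to vertex-TMS trials". Hypothesis 1b expects a larger LPP under parietal-TMS "during encoding on successful trials, relative to unsuccessful trials".
- Section 8.2 makes memory performance and the LPP the two primary outcomes, with alpha 0.025 each.
- Section 4 (Study Design) also describes comparing EEG across task and stimulation conditions with no split by success, and its EEG subsection allows averaging by trial type, accuracy or both. Neither passage is carried into Section 8.3.2 as a primary test, and no sensitivity analysis for the sorting is given.

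**The concern.** Stimulation site and task are assigned by design. Later success is not: it is an outcome that follows stimulation, and the plan's first hypothesis is that parietal-TMS changes it. If that hypothesis is true, some trials that would have been forgotten under vertex stimulation are remembered under parietal stimulation. They are the weaker trials among the remembered ones and would have been the stronger ones among the forgotten. Moving them across lowers the average strength of both cells.

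Two errors can follow for a primary endpoint. A real LPP rise that drives the memory gain can be largely cancelled within the sorted cells. And if memory improves by a route that leaves the LPP alone, both memory cells fall and the analysis can report an LPP suppression that did not occur.

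**Working it through.** **The plan's own figure.** With the smaller effect in Section 8.2, eta-squared 0.28, f-squared = 0.28/0.72 = 0.389. For a three-level within-subject factor with lambda = 32 x 0.389 = 12.44, df 2 and 62, alpha 0.025, the noncentral F gives power 0.809, so N = 32 reproduces. The G*Power settings are not stated and other variants give other sizes (a paired test gives 28). The effect size is for hippocampal fMRI activity, so it does not establish power for a success-sorted LPP.

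**Inputs from the documents.** N = 32; alpha 0.025; pooled over the two experiments, 30 + 30 = 60 stim-on memory trials per site (Table 1) and 4 x 15 = 60 without stimulation.

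**Assumptions not in the documents.**
- A memory trial succeeds when a normal memory strength passes a threshold. Single-trial LPP correlates rho with strength; rho = 0.3, 0.5, 0.8.
- Base success is 60%, and the gain is about 8 points. The gain is sized from Section 8.2: eta-squared 0.44 gives dz = sqrt(0.44/0.56) = 0.886. The SD of a difference of two proportions over 60 trials is sqrt(2 x 0.6 x 0.4/60) = 0.089, and 0.886 x 0.089 = 0.079.
- There is trial noise only, with no participant-by-site variation. Adding such variation would lower the power and false-rejection figures below but would not change the cell shifts.
- No FDR step is applied beyond alpha 0.025.

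**Cell shifts.** z(0.60) = 0.253 and z(0.68) = 0.468, so the strength shift is d = 0.214. Mean strength relative to the site's own mean is phi(z)/p in the successful cell (0.644 at 60%, 0.526 at 68%) and -phi(z)/(1-p) in the unsuccessful cell (-0.966 and -1.118).

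| Parietal minus vertex, in units of rho x d | Successful | Unsuccessful | All memory trials |
|---|---|---|---|
| LPP rise carries the memory gain | 1 + (0.526-0.644)/0.214 = 0.45 | 1 + (-1.118+0.966)/0.214 = 0.29 | 1 |
| Memory improves, LPP unchanged | -0.55 | -0.71 | 0 |

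The site main effect averages three cells, with spatial trials unaffected. If sorting did no harm, (1+1+0)/3 = 0.67 of the rise would remain. Under the first row (0.45+0.29+0)/3 = 0.25 remains. Under the second, (-0.55-0.71+0)/3 = -0.42 appears from nothing.

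**Rejection rates (simulation, alpha 0.025).**

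| | rho 0.3 | rho 0.5 | rho 0.8 |
|---|---|---|---|
| LPP carries gain: unsorted parietal vs vertex | 35% | 83% | 99.7% |
| LPP carries gain: planned site main effect | 4% | 12% | 42% |
| LPP unchanged: unsorted | 2-3% | 2-3% | 2-3% |
| LPP unchanged: planned site main effect (negative) | 12% | 36% | 92% |

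Check of the unsorted row at rho 0.5: the rise is 0.5 x 0.214 = 0.107 trial-SD and its standard error is sqrt(2/60/32) = 0.0323. The noncentrality is therefore 3.32 and the power 83%.

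**Other mechanisms.**
- LPP up by 0.11 SD on all memory trials, memory unchanged: the planned site main effect has about 81-85% power, unsorted about 85%. A rise of almost the same size (0.107) gave 12% above, so that loss comes from the conditioning and not from smaller cells.
- LPP up by 0.17 SD on successful trials only: the successful-minus-unsuccessful contrast has about 60-70% power, the 3x3 interaction about 81%, and the unsorted test about 78%.
- For that contrast under the first model, the movement is 0.45 - 0.29 = 16% of the rise, with power about 3% at rho 0.5. Over base success of 50, 60, 70 and 80% the movement is 4, 16, 28 and 43%. A two-state recollection model with 25% guessing gives 46-96%. When the LPP is unchanged the contrast rejects in about 2-5% of runs.

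The 3x3x2 model was not simulated. It carries the same sorting factor with half the trials per cell.

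**The case against.** The best defence is that the plan asks about EEG markers of successful memory, and hypothesis 1b is explicitly about successful relative to unsuccessful trials. If TMS acts on the LPP only when encoding succeeds, the sorted contrast and the interaction detect it. If the LPP rises uniformly without a memory change, the site main effect also does well. Both points stand, and they limit the claim.

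The documents give neither a base success rate nor an LPP-memory correlation, so every rate above is conditional on the model. That stands too.

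It is also unclear that TMS is expected to change the variable actually used for sorting. The EEG subsection of Section 4 sorts memory trials by item recall, hypothesis 1a concerns context recollection, and Section 3 lists both. This is a fair gap, but it does not protect the plan: the synopsis hypothesises better memory performance generally, and an undefined sort is itself something to settle.

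Finally, Section 4 does mention unsorted comparisons. Because Section 8.3.2 does not adopt one, the primary LPP inference still rests on the sorted model.

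**Conclusion.** The concern holds for the primary LPP model. Its trial-type factor conditions on a post-stimulation outcome that the plan expects TMS to move, and no unsorted LPP test is named. The harm falls on the site main effect. At an assumed correlation of 0.5 it has about 12% power against 83% unsorted when the LPP carries the memory gain, and about 36% false negative-direction findings when only memory improves. These figures rest on the threshold model, the 60% to 68% success rates and noise at trial level only.

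A reader might infer more than this:
- That the successful-minus-unsuccessful contrast is the primary test. It is the wording of hypothesis 1b, but Section 8.3.2 puts its focus on the site main effect.
- That this contrast barely moves whenever the LPP truly rises. That is so when the LPP carries the memory gain at mid-range success rates, or when the rise is uniform. It is not so under the success-specific effect that hypothesis 1b describes.
- That the contrast readily gives false positives. Under the threshold model it shifts little when the LPP is unchanged. Only an extreme case (60% to 75% at correlation 0.8) reached 14%.

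The documents do not support a claim that the planned LPP analysis fails under every mechanism. They do show that its validity depends on a mechanism the plan has not established.

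**What to change.** Amend Section 8.3.2 before analysis:

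1. Make the confirmatory encoding-LPP test parietal versus vertex over all artifact-free stim-on memory-encoding trials, not sorted by later success. For Objective 2, test site by timing on the same unsorted trials.
2. Report (all memory minus spatial) x (parietal minus vertex) as the task-specificity test. It cancels stimulation-evoked activity common to both tasks, but it assumes that activity is equal in both. It has less power, about 49% at correlation 0.5.
3. Keep the successful/unsuccessful analysis for hypothesis 1b as supportive, and state that it conditions on a post-stimulation outcome.
4. Give one definition of a successful trial (item recognition or context recollection) and use it throughout.

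The cost is SAP wording; the data are the same. An effect confined to successful trials is diluted by the success rate: 0.17 SD at 60% success becomes 0.60 x 0.17 = 0.10 SD over all memory trials, which in the model above still leaves about 78% power. The simple parietal-versus-vertex test does not remove evoked activity that differs between coil positions, so item 2 should be reported beside it.

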TMS will be paired with task trials and consist of 2-second trains of continuous theta burst stimulation (cTBS; see Study Procedures). In Experiment 1, TMS will be delivered during the rest phase immediately prior to trial onsets (Figure 2). In Experiment 2, TMS pulses will occur during the trial while participants are actively engaged in the task (Figure 2). The order of experiments will be counterbalanced across subjects within each session. TMS will be delivered to an episodic memory network-connected location in posterior parietal cortex (see 4.4.2. TMS, below) or to the vertex as an inactive control condition, and the order of stimulation location will be counterbalanced across TMS/EEG sessions. One-third of trials will contain no stimulation as an additional control to examine behavioral and neural effects in the absence of the TMS sensory artifact (Table 1). Participants will then be tested on encoded items, also with EEG recording. EEG data will be examined in an event-related design, with timeseries following trial onsets compared across task (memory encoding, spatial processing, and memory retrieval) and stimulation (parietal-TMS, vertex-TMS, and no-TMS) conditions.

Figure 2. Experiment Design

Recruitment

Healthy participants will be recruited from the pool of individuals self-referring to the study directly and via the NIH Clinical Research Volunteer Program and via advertisements that will be pre-approved by the IRB. Although NIH employees will be allowed to participate, no direct solicitation of employees/staff by supervisors or co-workers will take place. Any recruitment material will be IRB approved. Participants who indicate interest will be pre-screened by phone. Pre-screening questions are listed in Appendix B. IRB-approved ads will be posted on NIH listservs with the permission of the moderator and IRB required statement on how the receiver was identified. Listservs may include NIH sponsored recruitment list serves such as (NIH HV recruitment list serv). Listserv announcement will include:

“You are receiving this message because your email address is included in the above NIH Listserv mailing list. The purpose of this message is to inform you of studies that are recruiting

Abbreviated Title: Task-dependent TMS and memory

Version Date: 11.15.22

volunteers at NIH, Bethesda, Maryland. The moderator of the listserv mailing list has permitted its use for this distribution”.

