Memory Task: This is a test of episodic memory, including item recognition and context recollection^{30,52,53}. In the task, participants will be shown a series of objects in one of four quadrants on the screen. They will be instructed to remember the objects and where they were located, both of which will be tested later. To ensure attention and for consistency with the spatial task (see below), they will be asked to indicate by button press whether the object is primarily used outdoors (e.g., a baseball) or indoors (e.g., a television). During the encoding phase, each object will be presented for 4 seconds with 4 seconds between trials. In Experiment 1, TMS will occur during a 2 second cue before each trial and in Experiment 2, TMS will occur in the first 2 seconds of stimulus object presentation. There will be 180 encoding trials, interspersed with 180 trials of the spatial task (described below). Trial order will be randomized. The retrieval phase will occur following the end of encoding. Participants will be shown, sequentially and in randomized order, the 180 encoded objects and 180 new lure objects, for a total of 360 trials. For all trials, they will respond with whether the object was old (previously seen) or new (not previously seen) and their confidence on a scale of 1-6 (1=confident new,

Abbreviated Title: Task-dependent TMS and memory

Version Date: 11.15.22

6=confident old) as a measure of item recognition. If the object was previously seen, participants will then be asked which quadrant the item was presented in to provide a measure of context recollection. We will use two different versions of the task with different and non-overlapping sets of objects at the two test sessions and the order of versions will be counterbalanced across participants.

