Spatial Task: This is a test of spatial processing, which will serve as a control task to isolate neural markers of memory engagement, versus engagement in any task with similar visuospatial qualities. Notably, spatial processing activates a network of frontoparietal including the posterior parietal cortex regions^{54,55}, allowing it to further serve as a control to isolate hippocampal network effects of TMS from the local effects of TMS on the stimulated region. In each trial of this task, participants will be shown an arrow pointing to one corner of the screen and displayed in one of four quadrants. They will be instructed to indicate by button press whether the arrow points to the corner in which it is displayed (“match,” e.g. pointing to the upper right corner in the upper right quadrant) or a different corner (“no-match,” e.g. pointing to the upper right corner in the upper left quadrant). Accuracy of match/no-match responses will be assessed. Each arrow will be presented for 4 seconds with 4 seconds between trials. In Experiment 1, TMS will occur during a 2 second cue before each trial and in Experiment 2, TMS will occur in the first 2 seconds of stimulus presentation. There will be 180 trials, interspersed with encoding trials of the memory task. We will use two different versions of the task at the two test sessions.

TMS

The parietal target will be the region of the left posterior parietal cortex with the greatest connectivity with the left hippocampus derived from the baseline resting-state fMRI session³¹. This region was chosen because of its dense connections with the hippocampus^{56,57}. Thus, stimulation of this location can modulate function of the hippocampal-cortical network^{30-36,38}.

The control target will be vertex, a commonly used active control site which does not influence neural or behavioral activity⁵⁸.

TMS targets will be marked in the participant’s anatomical MRI volume and located with a frameless stereotaxic system. If any experiment, for any reason, fails to produce useful individual targets, a literature-based location for the parietal cortex³¹ will be used as our location of stimulation. To reduce the influence of diurnal variations in the responsiveness to neuroplasticity protocols⁵⁹, we will make every effort to test subjects during the same time of day.

[figure not shown]

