Devices determined to be used on label or other exempted devices pursuant to 21CFR812.2(c):

GE Discovery MR 750 System-3T. 510k: K163331

- a. This device and associated system carries an FDA 510(k) clearance . The Sponsor has determined that the device is used in the trial in accordance with this label.

Primary Objective

Primary Objective 1: Investigate how TMS modulates EEG neural measures of successful memory and the association of this modulation with behavioral performance

- Hypotheses

Abbreviated Title: Task-dependent TMS and memory

Version Date: 11.15.22

- Network-targeted parietal-TMS will improve memory performance (context recollection; Primary Outcome Measure 1) on parietal-TMS relative to vertex-TMS trials
- Relative to vertex-TMS, parietal-TMS will also increase the Late Positive Posterior ERP (Primary Outcome Measure 2) and theta power (Secondary Outcome Measure 1) during encoding on successful trials, relative to unsuccessful trials
- The EEG effects will correlate with memory improvement (Correlation, Primary Outcome Measure 1 and Primary Outcome Measure 2/Secondary Outcome Measure 1)
- Additionally, parietal-TMS will alter EEG functional connectivity patterns (Exploratory Outcome Measure 1) at encoding during successful trials relative to unsuccessful trials
- Parietal-TMS will not influence neural activity or accuracy for spatial trials, relative to vertex-TMS and no-TMS

Primary Objective 2: Examine how memory task state influences susceptibility to plasticity via TMS and determine the optimal neural state for improving memory

- Hypotheses
 - Network-targeted parietal-TMS during memory encoding will have a larger effect on source recollection (Primary Outcome Measure 1), relative to pre-trial parietal-TMS and vertex-TMS during encoding
 - Exploratory Analyses:
 - Parietal-TMS during memory encoding will increase the Late Positive Posterior ERP (Primary Outcome Measure 2) and theta-power (Secondary Outcome Measure 1), relative to pre-trial parietal-TMS and vertex-TMS during encoding
 - Additionally, parietal-TMS will alter EEG functional connectivity patterns (Exploratory Outcome Measure 1) during later-remembered trials, relative to pre-trial parietal-TMS and vertex-TMS during encoding
 - Network-targeted TMS will not influence neural activity during arithmetic trials, relative to vertex-TMS and no-TMS

Exploratory Objective:

Search for MRI predictors of the effects of parietal TMS

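### Section 8.3.2 reads a three-level site main effect (parietal/vertex/none) as the effect of parietal-TMS, but specifies no parietal-versus-vertex test of hypotheses 1a and 1b

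*Combined protocol and SAP*

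**What the plan says.** The hypotheses are comparisons with vertex. Section 4 (Primary Objective) states 1a as: "Network-targeted parietal-TMS will improve memory performance (context recollection; Primary Outcome Measure 1) on parietal-TMS relative to vertex-TMS trials". Section 8.1 repeats it. Hypothesis 1b says that parietal-TMS, relative to vertex-TMS, raises the late positive posterior ERP and theta power at encoding on successful relative to unsuccessful trials.

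For Objective 1, section 8.3.2 plans a 3x3 ANOVA on each outcome: trial type (successful, unsuccessful, spatial) by site (parietal, vertex, none). One sentence names the term to be read: "We will particularly focus on the main effect of stimulation site to determine". The same sentence then says what that term and the interaction are taken to show: "the influence of parietal-TMS on memory performance and its neural correlates, and the interaction effect to determine the task specificity of TMS effects". The threshold is 0.025 after FDR, and the comparisons in the FDR family are not listed. No planned contrast or pairwise follow-up is named. The parietal-minus-vertex difference enters an analysis only in the exploratory MRI correlations (sections 8.1 and 8.3.4).

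Three design statements in section 4 bear on this:

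- On the no-stimulation level: "One-third of trials will contain no stimulation as an additional control to examine behavioral and neural effects in the absence of the TMS sensory artifact".
- On vertex, described as "a commonly used active control site which does not influence neural or behavioral activity".
- On sessions: "the order of stimulation location will be counterbalanced across TMS/EEG sessions". Parietal and vertex stimulation are therefore given on different days. By Table 1, each day also has its own Stim Off trials.

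**The concern.** A main effect of a three-level factor says that the three means are not all equal. It does not say which differ. If stimulation at either site disturbs performance or the EEG through clicks, scalp sensation or distraction, both active levels move away from none together. The site term then becomes significant with parietal equal to vertex. Under the reading given in 8.3.2, that result would be reported as an influence of parietal network stimulation, which is the trial's central claim.

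The interaction does not fill the gap. Hypothesis 1b is one degree of freedom: (parietal minus vertex) by (successful minus unsuccessful). The planned interaction has four degrees of freedom, includes the spatial and no-TMS cells, and is described as showing task specificity.

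Pairwise follow-up may well be intended. Because it is not written down, the choice of pair, outcome and accuracy denominator is left until the data are seen.

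**Working it through.** **1. The plan's own figure.** Section 8.2 gives n = 32 for η² = 0.28 (the smaller of its two effects), power 0.80 and α = 0.025. With f² = 0.28/0.72 = 0.389, λ = f²·N and df = 2 and 2(N−1), power is 0.793 at N = 31 and 0.809 at N = 32. So 32 is reproduced for a 2-df within-person effect. The match is not unique, because 8.2 does not state the number of measurements, the correlation or the effect-size option. The same formula with 1 df gives 28, and with 4 df gives 38.

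**2. Site main effect with parietal equal to vertex (late positive ERP).** Assumptions: the unit is the residual SD of a cell mean, cell residuals are independent and equal, and both active sites shift from none by the same d on all trial types. Averaging three trial types gives a residual variance of 1/3 per site mean. The squared deviations of (d, d, 0) from their mean sum to 2d²/3. Hence λ = 32 × (2d²/3)/(1/3) = 64d², with df 2 and 62.

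| Assumed shift d | λ | Site term significant | Session SD 0.5 | Session SD 1.0 |
|---|---|---|---|---|
| 0.2 | 2.56 | about 18% | about 12% | about 7% |
| 0.3 | 5.76 | about 42% | about 31% | about 13% |
| 0.4 | 10.24 | about 71% | about 58% | about 28% |
| 0.5 | 16.00 | about 91% | about 82% | about 51% |

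The session columns are simulated. They add a person-by-session deviation shared by all cells of that day, with the no-TMS cell averaging both days. In every row the parietal-minus-vertex contrast is significant in about 2.5% of runs.

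The table has no FDR step. With Benjamini-Hochberg over an assumed 4 to 12 tests that are otherwise null, the column without session variation falls to roughly 4–8%, 15–26%, 39–52% and 68–79%.

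**3. Interaction.** Under the same uniform shift it stays nominal, at about 2.4%. It is inflated only if the artifact differs by trial type. With a shift on successful trials only, of 0.5 or 0.8 SD, it is significant in about 18% or 54%. A shift on both memory trial types but not on spatial trials gives about 19% or 54%. The 1b contrast stays near 2.5% throughout.

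**4. A conditional point on accuracy.** Section 3 defines accuracy as "Percentage of successful (later remembered hit and correct rejection) vs unsuccessful (forgotten miss and false alarm) trials". Suppose context recollection enters the 3x3 as a successful percentage p and an unsuccessful percentage 100 − p, next to spatial accuracy q. The mean over trial types at a site is (p + 100 − p + q)/3 = (100 + q)/3, which does not contain p. With assumed q = 90, a rise in p from 60 to 65 leaves it at 190/3 = 63.3. On that coding the site main effect cannot show a memory gain, and any signal falls in the interaction.

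**5. Power of the contrasts.** For 1b with an assumed gain of 1.1 SD on successful parietal trials, the double difference has SD √4 = 2, so dz = 0.55 and power is 77%. With noise scaled to an assumed 18 successful and 12 unsuccessful trials it is about 67%. The 4-df interaction has 87% and 86% if no-TMS equals vertex, and 73% and 71% if no-TMS lies midway.

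For 1a with an assumed gain of 5 points (60% baseline, between-person logit SD 0.5), the contrast has about 49% power in one experiment (30 trials per site) and 83% with both pooled (60 trials). An assumed session SD of 5 points lowers these to 38% and 57%.

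**6. What 8.2's power means for the contrast.** If η² = 0.28 belongs to parietal versus vertex, dz = √0.389 = 0.62 and power at n = 32 is 0.873. If it is the 2-df site effect with only parietal differing, then 4dz²/3 = 0.389, dz = 0.54 and power is 0.755.

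**The case against.** The strongest reply is that the protocol treats vertex as inactive. If vertex-TMS equals no TMS, a site effect is a parietal effect, and the omnibus interaction can have more power than the contrast (87% against 77% above). This stands as far as it goes. However, section 4 adds the no-stimulation trials because active stimulation carries a sensory artifact, so the plan does not itself treat the two controls as interchangeable.

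A second reply is that the rates rest on assumed shifts and leave out parts of the design. This also stands. A reader might take 18–91% as the trial's false-positive rate. The documents do not support that: they give no artifact size, sessions differ by site, and FDR is planned. The rates show that the term can mislead, not how often it will.

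A third reply is that 1b is an interaction hypothesis and an interaction is planned. A reader might infer that this test is inflated too. Under a uniform shift it is not, and inflation needs an artifact that differs by trial type. What remains is that the 4-df term does not isolate 1b.

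Fourth, section 3 does not say that the two percentages enter as separate cells. Its definition also counts correct rejections and false alarms, which come from lures with no stimulation site. The claim that the main effect cannot detect a memory gain therefore holds on one coding only.

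**Conclusion.** The concern holds in a limited form. For Objective 1 the plan ties its conclusion about parietal-TMS to a 2-df site term, while hypotheses 1a and 1b are parietal versus vertex and no test of that comparison is specified. Followed as written, 8.3.2 could credit parietal stimulation with a difference between TMS and no TMS.

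The size depends on an artifact that the documents do not quantify. For assumed shifts of 0.2 to 0.5 SD on the late positive ERP, the site term is significant in about 18–91% of runs without session variation and about 7–51% with a session SD of 1.0, before FDR. The contrast stays near 2.5%. If vertex-TMS equals no TMS, the size is nil.

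A reader might also infer that 32 participants are too few. That is not shown: the power of the contrast depends on which effect the cited η² describes and on session variation, and the documents settle neither. The data to be collected support the right test, which only has to be named.

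**What to change.** Add to 8.3.2 for Objective 1:

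> Hypothesis 1a will be tested by the within-person contrast parietal-TMS minus vertex-TMS on context recollection in stimulated memory trials, as one accuracy score per person and site. Hypothesis 1b will be tested by (parietal-TMS minus vertex-TMS) x (successful minus unsuccessful) on the late positive posterior ERP at encoding, and likewise for theta power as secondary. The contrasts on the two primary outcomes are two-sided at the planned 0.025 per outcome. The 3x3 ANOVA, the no-TMS comparisons and the spatial trials are supporting evidence; a site main effect or interaction alone will not be read as a parietal effect.

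Before analysis the sponsor should also name:

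- the FDR family;
- whether the two experiments are pooled;
- the recollection denominator, since section 4 gives none and asks location only conditionally: "If the object was previously seen, participants will then be asked which quadrant the item was presented in";
- whether the same-session Stim Off trials are used to adjust for session.

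Section 8.2 should say which effect the stated 80% power refers to.

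The cost is text only, with no new data and no proposed change in n. The real downside is power: the 1b contrast can be weaker than the omnibus interaction when no-TMS equals vertex, and session variation lowers power for 1a.
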